##### **- Preoperative measures (for all groups):**

- Medical and dental history will be obtained from all patients participating in this research. Clinical and radiographic evaluation for each tooth included in this study will be recorded.
- Pain scale chart will be given to each patient to rate his /her pain level before endodontic treatment as preoperative reading on an NRS scale.
- Tooth will be anaesthetized using 1.8 ml Mepivacaine HCl 2% - Levonordefrin 1:20000 (Carpule Mepecaine-L, Alexandria Company for Pharmaceuticals and Chemical Industries, Egypt).
- The tooth will be isolated with rubber dam to maintain aseptic field, after isolation the tooth and surrounding field will be disinfected by a protocol using 3% hydrogen peroxide 2.5% sodium Hypochlorite before and after coronal access cavity preparation.
- The initial sample S1 will be collected from root canals before preparation using sterile # 15 paper points.

- Sterile saline solution will be injected in the canals followed by the insertion of a #15 K-file (Mani, Japan) to at least 1 mm short of the apex as confirmed by apex locator (Root ZX, J.Morita USA, Irvine, CA) to facilitate the insertion of the paper points to collect the samples.
- Each paper point will remain in place for at least 1 minute then immediately placed in test tubes containing reduced transport fluid and sent to the Microbiology Laboratory, Faculty of Medicine, Cairo University for microbiologic processing.
- Root canals will be mechanically prepared in a crown-down approach using the rotary files (M-Pro file system) in an endodontic motor (X-Smart, Dentsply Maillefer, USA) according to the manufacture instructions.

The following sequence will be used for all groups:

- # 18 file taper (orifice opener) 0.09 will be used to prepare two thirds of estimated working length.
- # 20 file taper 0.04 will used to full working length.
- #25 file taper 0.06 will used to full working length.
- #35file taper 0.04 will used to full working length.
- The canals will be thoroughly irrigated for 1 minute between every two subsequent files using 2 ml of 2.5% NaOCl.
- After complete preparation all canals will be flushed with EDTA followed by sterile saline.
- **Intervention for test group A**
  - After complete preparation, the canals will be flushed using 5 ml of Nano chitosan (Nano tech, Egypt) in a plastic syringe using Navitip needles (Ultradent, South Jordan,UT).

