**Secondary outcome:**

- **Postoperative pain:** will be recorded on a Numerical Rating scale (NRS), pain intensity will be recorded preoperatively and postoperatively after 6, 12, 24, 48, 72 hours and 7 days. The NRS consists of a 10-cm line anchored by two extremes "No pain" and "pain as bad as could be", patient will be asked to choose the mark that represent their level of pain. Pain level will be assigned to one of 4 categorical scores: **1**, None(0); **2**, Mild(1-3); **3**, Moderate(4-6); **4**, Severe (7-10).

Outcome	Tool	Unit	Time
Postoperative pain	Numerical rating scale NRS 	Categorial data	Immediately after treatment and Up to 7 days after endodontic treatment

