### 13. Participants time line

STUDY PERIOD									
Time point	T0	T1	F1	F2	F3	F4	F5	F6	F7
Activity									
Enrollment									
Eligibility criteria	x								
Informed consent		x							
Allocation		x							
Intervention									
Access		x							
Initial sample		x							
Cleaning and shaping		x							
Final sample		x							
Obturation		x							
Assessment									
Intracanal bacterial count		x							
Postoperative pain			x	x	x	x	x	x	x

T0: Enrollment of the patient after diagnosis and radiographic evaluation.

T1: Signing the informed consent and allocation of the patient to either intervention or control group. Starting the procedure, taking the first root canal sample before cleaning and shaping, second root canal sample after cleaning and shaping, obturation.

F1: Patients will be asked to evaluate their postoperative pain levels using a numerical rating scale (NRS)

F2: similarly, at 6 hours.

F3: similarly, at 12 hours.

F4: similarly, at 24hours.

F5: similarly, at 48 hours.

F6: similarly, at 72 hours.

F7: similarly, at 7 days.

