### **C) Data collection, management, and analysis:**

#### **18. Data collection methods:**

- Base line data will be recorded on a personal history chart prior to clinical examination.
- Antimicrobial efficacy will be measured by counting the number of colony forming units CFU of bacteria after cultivating the collected samples.
- Paper based pain scale (VAS) assessments will be filled by the patient preoperatively, and postoperatively after 6, 12, 24, 48,72 hours and after7 days.

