#### **20. Statistical methods:**

- Data will be analyzed using IBM SPSS advanced statistics (Statistical Package for Social Sciences), version 21 (SPSS Inc., Chicago, IL). Numerical data will be described as mean and standard deviation or median and range. Data will be explored for normality using Kolmogrov-Smirnov test and Shapiro-Wilk test. Comparisons between 4 groups for normally distributed numeric variables will be done using the ANOVA while for nonnormally distributed numeric variables will be done by Kruskal Wallis test. A p-value less than or equal to 0.05 will be considered statistically significant. All tests will be two tailed.
- Categorical data will be described as numbers and percentages and comparisons will be done by chi square test or fisher exact as appropriate

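### As written, pain severity most naturally goes to an unordered chi-square or Fisher test at six or seven times, which costs power and leaves multiplicity open

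*Combined protocol and SAP*

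**What the plan says.** Section 7 gives one secondary objective: how often postoperative pain occurs and how bad it is.

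Section 12 (Secondary outcome) sets a 0-10 scale and then says "Pain level will be assigned to one of 4 categorical scores": none, mild, moderate and severe. Its table classes the outcome as categorical. On timing, the text says "pain intensity will be recorded preoperatively and postoperatively after 6, 12, 24, 48, 72 hours and 7 days", while the table says "Immediately after treatment and Up to 7 days after endodontic treatment".

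Section 11.a has each patient "rate his /her pain level before endodontic treatment as preoperative reading on an NRS scale".

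Section 20 does not name pain. For categorical data it says "Categorical data will be described as numbers and percentages and comparisons will be done by chi square test or fisher exact as appropriate". For numeric data it offers ANOVA, or else "nonnormally distributed numeric variables will be done by Kruskal Wallis test". Significance is p at or below 0.05, two-tailed. It contains no ordinal method for banded data, covariate, repeated-measures method, lead time point or multiplicity rule.

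Three descriptions of the readings do not agree:
- Section 13 schedules seven postoperative readings, F1 to F7. F1 has no stated time, and no preoperative pain reading appears.
- Section 18 lists a preoperative and six postoperative readings.
- Section 18 begins "Paper based pain scale (VAS) assessments will be filled by the patient preoperatively", whereas sections 11.a, 12 and 13 call the scale an NRS.

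**The concern.** Chi-square and Fisher treat the four levels as labels. Shuffle none, mild, moderate and severe, and the p-value does not change. Neither test can use the preoperative score, which the trial collects anyway. With 17 to 20 patients per group, discarding both the order and the baseline weakens a comparison of severity.

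A separate problem is that the same comparison is made six or seven times at 0.05, with nothing to say which time carries the claim. A chance finding at one time could be reported as a pain benefit.

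Because pain is not named in section 20, the choice between banded and numeric analysis is also open until after the data are seen.

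**Working it through.** **The plan's own figure.** There is none for pain. Section 14 sizes the trial on bacterial count, with a difference of 75 and SD of 75. The normal approximation gives n = 2 × (1.960 + 0.842)² / (75/75)² = 15.7, so 16 per group. The noncentral t calculation gives power of 78.1% at 16 and 80.7% at 17, so 17 is reproduced. Then 17 / (1 − 0.15) = 20. This fixes the group sizes used below and says nothing about pain.

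**Tests compared at one reading.**
- Chi-square: Σ(O − E)²/E, with (4 − 1)(4 − 1) = 9 df.
- Kruskal-Wallis: H = 12/(N(N + 1)) × ΣRᵢ²/nᵢ − 3(N + 1), corrected for ties, 3 df. It is applied to the bands or to the scores.
- Rank ANCOVA: ranked score on group and ranked preoperative score, with an F test on 3 df for group.

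**Inputs.** All are assumptions. Latent normal scores are rounded and clipped to 0-10, with mean 3 and SD 2.3. One of four arms is 2 points worse, and the correlation with preoperative pain is 0.4. There were 4,000 simulated trials (800 for Fisher).

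| Test | 17 per group | 20 per group |
|---|---|---|
| Chi-square on bands | 40% | 48% |
| Fisher on bands | 40% | 48% |
| Rank test on bands | 61% | 70% |
| Kruskal-Wallis on scores | 67% | 76% |
| Rank ANCOVA | 74% | 83% |

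With no true difference, chi-square, both Kruskal-Wallis versions and rank ANCOVA rejected in 3.8-5.1% of trials.

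**Sensitivity, 20 per group** (chi-square / rank test on bands / Kruskal-Wallis on scores / rank ANCOVA).
- SD 1.5: 86 / 97 / 99 / 100%.
- SD 3: 29 / 48 / 51 / 58%.
- 1-point effect: 12 / 20 / 22 / 27%.
- Rank ANCOVA against Kruskal-Wallis by baseline correlation: 77% v 77% at 0.1, 78% v 76% at 0.2, 92% v 76% at 0.6.
- Different inputs (bands 30/35/25/10%, one arm better by a common odds ratio of 3, 4 or 6): chi-square 26, 40, 62%; rank test on bands 42, 62, 83%.

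**Multiplicity.** If readings were independent, the chance of at least one false positive is 1 − 0.95⁶ = 26.5% for six and 1 − 0.95⁷ = 30.2% for seven. Readings on one patient are correlated. With simulated scores at six times and between-time correlation 0.5-0.7, at least one unadjusted chi-square test was significant in 19.5-21.3% of null trials.

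**Does one summary across times clearly win?** Power at 17 / 20 per group, six times, between-time correlation 0.5-0.7:

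| Assumed effect | 6 h lead, rank ANCOVA | Rank ANCOVA at each time, Holm | Baseline-adjusted mean |
|---|---|---|---|
| Fades from 2 to 0 points | 73-75% / 81-82% | 67-70% / 75-83% | 52-65% / 58-78% |
| 2 points at 6 h only | 75-77% / 81-83% | 50-51% / 59-61% | 10% / 9-12% |
| 1.5 points throughout | 45-48% / 54-58% | 52-59% / 63-67% | 66-81% / 77-88% |

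A joint repeated-measures test had 70-80% / 81-88% for the fading effect. With serially decaying correlation it fell to 44% / 52%, against 60% / 71% for Holm. The ranking depends on the shape of the effect, and the documents give no time course.

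**The case against.** **The plan does not commit pain to chi-square.** Section 12 records an intensity and section 20 already offers Kruskal-Wallis, so the raw scores could be analysed as numeric. This is fair. A reader might infer that the plan fixes the unordered test, but it only points there through the categorical label. Under the numeric reading order is kept, yet baseline, lead time and multiplicity remain unaddressed.

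**Chi-square or Fisher is right for half the objective.** This stands. For any pain versus none there is no order to lose, and the objective names occurrence as well as severity.

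**The power gain is conditional.** This also stands. The inputs are assumed, a 1-point effect defeats every method, and baseline adjustment gains almost nothing if the correlation is near 0.1. The rank advantage also presumes that arms differ by a shift along the severity scale. Section 6 cites a trial with little postoperative pain, so small differences are plausible.

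**Pain is not confirmatory.** The hypothesis in section 7 and the sample size in section 14 concern antimicrobial efficacy only. Labelling by-time pain results exploratory would therefore be an adequate answer to multiplicity, provided it is stated in advance.

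**A four-group test is not a comparison with NaOCl.** True. The remedy below does not by itself supply a rule for the three comparisons with NaOCl, or for missing readings.

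**Conclusion.** The point holds as a weakness worth correcting in the secondary analysis. On the natural reading, severity is tested without its order and without the preoperative score. Under the base assumptions, moving from chi-square to rank ANCOVA raises power from about 40% to 74% at 17 per group and from about 48% to 83% at 20. Most of that gain comes from respecting order and using the scores. The baseline part depends on a correlation that the documents do not give. Six unadjusted tests carry roughly a one-in-five chance of a false pain finding under moderate correlation.

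Three stronger conclusions that a reader might infer are not supported:
- Each chi-square test is not invalid. It keeps about its 5% level, so ignoring order costs power and does not by itself create false positives.
- The primary outcome is not touched.
- No way of combining times can be ruled out. The mean over seven days does badly for an early, brief effect and best of the three tabulated options for a sustained one.

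The differences in scale name and reading schedule are clerical, but they leave the number of tests unclear.

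**What to change.** In section 20, name pain and state:

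1. **Severity** is compared on the 0-10 scores with an order-respecting method adjusted for the preoperative score. Rank ANCOVA is one example, with Kruskal-Wallis, already in the plan, as the unadjusted version.
2. **Incidence** of any pain versus none keeps chi-square or Fisher.
3. **Times**, decided before data are seen: either name one lead time point or one overall test (repeated-measures or baseline-adjusted mean), with Holm for the remaining times, or label the by-time results exploratory.
4. **Description**: show the four bands, and report by group the ibuprofen tablet count that patients already record. Analgesic use can mask a difference. If a score of 4 or more led to a 1- or 2-point drop at the next reading (assumed), a 1.9-point difference at 12 h would appear as 1.5 or 1.2.

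Reconcile sections 11.a, 12, 13 and 18 on the scale name and on the number and timing of readings, including the preoperative one and F1. Section 12's table may supply F1's time. Section 12 also describes its NRS as a 10-cm line. If marks are continuous, the bands leave gaps between 3 and 4 and between 6 and 7.

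The cost is a little more analysis and some wording, with no new data. The real risk is a poor choice of lead time or summary: with an effect at 6 h only, a 24 h lead has 3-6% power.

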#### **D) Data monitoring:**

- The data will be monitored by the main supervisor ([name]) for any modification of the trial if needed

#### **21. Harms:**

- Any temporary or permanent adverse effect will be recorded and documented and treated.

#### **22. Auditing:**

- The study supervisors: [name]. [name] and, dr [name] will regularly assess the trial process and documents. "Adherence to trial interventions and policies to protect participants, including reporting of complications and their treatments. ". Auditing of the study design will be done by the evidence based committee.

## **IV. Ethics and dissemination**

### **23. Research ethics approval:**

- "This protocol and the template informed consent form will be reviewed by the Ethics Committee of Scientific Research - Faculty of Dentistry, Cairo University".

### **24. Protocol amendments:**

- "Any amendment to the protocol which may affect the conduct of the research, potential benefit of the patient or may have impact on patient safety, inclusive changes of study objectives, study design, sample sizes, study procedures, or significant administrative aspects will demand a formal modification to the protocol". Such modifications will be agreed upon by the Council of the Department of Endodontics.

### **25. Consent:**

- The treatment plan will be fully explained to the patient and after educating the patient with all the needed data and complications that could occur, an Arabic consent form will be signed by patients who are willing to participate.

### **26. Confidentiality:**

- "All study- associated information will be maintained securely. All participant data will be stored in locked lockers in areas with restricted entrance. All experimental specimens, reports, data gathering process, and administrative charts will be recognized by a coded ID number only to keep participant exclusiveness. All documentation that comprise personal identifiers including name, age, sex, identification number, address, phone number, work address will be secured disparately from study records identified by code number. All available databases will be secured with countersign- preserved entry systems".

### **27. Declaration of interests:**

- This study is a part of a PhD degree in Endodontics, Faculty of Dentistry; Cairo University. No financial conflict of interests is confirmed. The study is self-funded by the principal investigator.

### **28. Access to data:**

- "All Principal investigators will be given entrance to the data sets. All data sets will be kept secure. To ensure confidentiality, data dispersed to project team members will be blinded of any recognizing participant data".

### **29. Dissemination policy:**

- Study results will be published as partial fulfillment of the requirements for PHD degree in Endodontics.
- Topics proposed for presentation or publication will be expanded to the authors.

## **V. Appendices:**

**VI: Statement of originality:**

- Within the scope of our search no study evaluated the antimicrobial effects of Nano chitosan, Chlorhexidine, Chlorhexidine/ Nano Chitosan combination to those of NaOCl for irrigation in endodontic treatment of necrotic teeth in-vivo; therefore, this study is an original study.

